OBJECTIVES	
Primary Objective
 
Establish the recommended Phase II dose (RP2D) during the Safety Lead-In and to assess efficacy via objective response rate (ORR) via RECIST 1.1 during the Phase II study of entinostat in combination with nivolumab and ipilimumab in patients with advanced renal cell carcinoma who have progressed on nivolumab + ipilimumab regimen or nivolumab alone. 
Secondary Objectives
 
Characterize safety of entinostat in combination with nivolumab and ipilimumab or nivolumab aloneEstimate ORR via Immune Related Response Criteria (irRC)Estimate progression free survival (PFS) by RECIST 1.1 and irRCEstimate overall survival (OS) 
Exploratory Objectives Characterize PD-L1/2, immune cell subsets, and miRs in tumor and/or blood and correlation with response.

STUDY DESIGN	Originally this study was intended as a Phase II, open-label, safety, pharmacodynamics and efficacy study of entinostat in combination with nivolumab and ipilimumab in subjects with advanced renal cell carcinoma (RCC) who have progressed on ipilimumab + nivolumab regimen or nivolumab alone. The clinical study was composed of a two-stage Phase II portion. The Safety Lead-in was to establish the Recommended Phase II Dose (RP2D) in subjects with metastatic RCC. Subjects will be treated with oral entinostat every 7 days continuously, and with nivolumab at a dose of 3 mg/kg mg IV every three weeks in combination with ipilimumab at a dose of 1 mg/kg every 3 weeks × 4 doses. Then, nivolumab 480 mg will be continued every 4 weeks. Subjects that do not tolerate this dosing strategy may receive nivolumab 240 mg IV every 2 weeks. Therefore, each cycle is every 21 days × 4 cycles and then every 28 days thereafter. One dose level of entinostat will be tested in 6-patient cohorts with a dose de-escalation design (5 mg, 3 mg and 2 mg). The 5 mg dose represents 50% of the recommended entinostat

	
dose as single agent. The starting dose level of entinostat will be 5 mg PO every 7 days. The first dose level will have a minimum of 6 patients treated. If ≤ 1 dose limiting toxicity (DLT) is observed the study was to move to the Phase II portion and the 6 patients be included in Stage 1 of the Phase II portion. If >1 DLT is observed 6 additional patients will be treated at the lower dose level, etc. DLTs are defined in Section 5.2.1. Due to Funder decision, accrual will halt after enrollment of the safety lead in. This decision is a result of a shift in priorities at the Funder and not due to safety issues. Subjects currently on treatment will continue until criteria as defined in Section 6.2 is met.

KEY ELIGIBILITY CRITERIA See Section 3 for full eligibility criteria
	
 • Metastatic renal cell carcinoma with progressive disease on nivolumab + ipilimumab regimen or nivolumab alone. • Adequate hematologic, hepatic, and renal function is required. • ECOG performance status of 0-1. • Life expectancy of at least 6 months.

STATISTICAL CONSIDERATIONS
	
For the Safety Lead-in, up to 18 subjects could be enrolled. Entinostat will be tested in 3 dose level cohorts (5 mg, 3 mg, or 2 mg). The highest of 3 dose levels of entinostat (either 5mg, 3 mg or 2mg) that results in ≤ 1 out of 6 subject rate of DLT will be the RP2D. For Phase II, assuming a type I error rate of 5% and a power of 90% to compare an uninteresting objective response rate per RECIST 1.1 of 5% while declaring efficacy at 20%, Simon's optimal two stage design enrolls 21 patients in the first stage (with 6 of the 21 from the Safety Lead-in RP2D cohort). If at most one response is seen, then the trial is terminated for futility. Otherwise, accrual continues to a total of 41 patients. If at most 4 patients respond among the 41 patients, the combination would not warrant further investigation. If at least 5 patients respond, this therapy would warrant further investigation. The average sample size is 26.66 and the early termination probability is 71.70% for a drug with a response rate of 5%. All the calculations are based on the R function ph2simon from the package clinfun.

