5.1 Study Treatment Administration

5.1.1 Cycles 1-4 (cycle =21 days)

Drug	Dose	Route	Schedule ¹	Cycle Length
Entinostat	5mg, 3mg, or 2mg ²	PO	Days 1, 8, 15	21 days
Nivolumab	3 mg/kg	IV over 30 minutes	Day 1	
Ipilimumab	1 mg/kg ³	IV over 30 minutes	Day 1	

¹ A window of \pm 3 days may be applied to all study visits to accommodate observed holidays, inclement weather, scheduling conflicts etc. Date and time of each drug administration should be clearly documented in subject's chart or on drug diary and in the electronic case report forms (eCRFs).

² See Section 5.2 on the Safety Lead-In for determining the RP2D of entinostat

³ Use the subject's actual (not ideal) body weight for dosing as per the American Society of Clinical Oncology (ASCO) guidelines on dosing of obese adult subjects. If a subject's weight changes by more than 10% from Cycle 1 Day 1 the dose of nivolumab and ipilimumab should be recalculated.

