5.2 Safety Lead-In

Entinostat in combination with fixed dose nivolumab and ipilimumab will be tested using a 3+3 dose de-escalation design (5 mg, 3 mg and 2 mg). The starting dose level of entinostat will be 5 mg PO every 7 days, which is 50% of the recommended entinostat dose when used as single agent. Dose limiting toxicities (DLTs) will be evaluated during the first two cycles (6 weeks) of treatment. Each dose level will have up to 6 patients treated.

The trial will proceed in a 3+3 fashion. The study will recruit the first 3 patients starting at the highest dose level (5 mg). If there is 0 or 1 DLT, then the study will recruit additional 3 patients treated at that dose level. If \leq 1 DLT is observed after 6 patients at this dose, that will be the

RP2D. If any time at this dose level, more than 1 DLT is observed, then the accrual to this dose level will be stopped, and the study will be de-escalated to the next dose level (3mg).

This procedure is repeated at the second dose level cohort (3 mg). At this dose level, the study will study 3 patients first. If there is 0 or 1 DLT, then the study will recruit additional 3 patients treated at that dose level. If ≤ 1 DLT is observed after 6 patients at this dose, that will be the RP2D. If any time at this dose level, more than 1 DLT is observed, then the accrual to this dose level will be stopped, and the study will be de-escalated to the next dose level (2 mg).

Up to 6 patients will be enrolled and treated at the last dose level cohort (2 mg). At this dose level, the study will study 3 patients first. If there is 0 or 1 DLT, then the study will recruit additional 3 patients treated at that dose level. If ≤ 1 DLT is observed after 6 patients at this dose, that will be the RP2D. If any time at this dose level, more than 1 DLT is observed, then the accrual to this dose level will be stopped, and the study will be terminated and no RP2D can be reached.

For the Safety Lead-in, up to 18 patients could be enrolled. The RP2D will be the highest of these 3 dose levels of entinostat that results in ≤ 1 out of 6 subjects experience a DLT. The 6 subjects in the RP2D cohort will be included in Stage 1 of the Simon's optimal two-stage Phase II study.

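### The synopsis requires at least 6 patients at 5 mg with no look after 3, which contradicts the 3+3 stopping rule in Section 5.2

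*Combined protocol and SAP*

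**What the plan says.** **Synopsis, Study Design.** "One dose level of entinostat will be tested in 6-patient cohorts with a dose de-escalation design", with doses of 5, 3 and 2 mg. Then: "The first dose level will have a minimum of 6 patients treated". With at most 1 DLT the study was to proceed to Phase II. Otherwise: "If >1 DLT is observed 6 additional patients will be treated at the lower dose level, etc". There is no decision after 3 patients. The only cross-reference is to Section 5.2.1, for the DLT definitions.

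**Section 5.2, Safety Lead-In.** The design is labelled 3+3. At 5 mg, 3 patients are recruited, and 3 more follow only if 0 or 1 of them has a DLT. The size of a level is a ceiling: "Each dose level will have up to 6 patients treated". The stopping rule is continuous: "If any time at this dose level, more than 1 DLT is observed, then the accrual to this dose level will be stopped". For 3 mg and again for 2 mg it says: "At this dose level, the study will study 3 patients first".

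**Which text governs.** Footnote 2 to the dosing tables in Sections 5.1.1 and 5.1.2 reads: "See Section 5.2 on the Safety Lead-In for determining the RP2D of entinostat". Nothing says that Section 5.2 overrides the synopsis. The opening of Section 5 sends the lead-in reader to Section 5.1.

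**Common ground.** Both texts choose the highest dose with at most 1 DLT in 6 patients, and both cap the lead-in at 18.

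**The concern.** Six patients at 5 mg is a floor in the synopsis, while in Section 5.2 it is a ceiling with an early exit. If two of the first three patients have DLTs, the synopsis still calls for three more at that dose and Section 5.2 forbids them. A similar difference appears at the lower doses, where the synopsis sends 6 additional patients and Section 5.2 starts with 3.

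A site or study team working from the synopsis could therefore keep treating patients at a dose that has already failed its own DLT limit. The lead-in is the only part of the trial that will enrol, so this is the only dose-decision rule still in use.

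**Working it through.** **1. The plan's own figure.** Three dose levels of at most 6 patients give 3 × 6 = 18. This is the stated maximum, and it holds under either text.

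**2. When the texts conflict.** They conflict when a second DLT is seen at 5 mg before patient 6 has entered. How early it can be seen depends on how patients 4 to 6 enter, so two cases bracket it. In both, the first three are fully observed before patient 4 enters.
- *Together:* patients 4 to 6 enter as a block. Conflict requires at least 2 DLTs in the first 3.
- *One at a time:* each is fully observed before the next enters. Conflict requires at least 2 DLTs in the first 5.

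**3. Inputs.** The documents give no DLT rate, so true rates p of 10% to 50% are assumed, with independent patients. With X the number of DLTs among n patients, P(X ≥ 2 | n) = 1 − (1−p)ⁿ − n·p·(1−p)ⁿ⁻¹.

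| p | ≥2 of 3 | ≥2 of 4 | ≥2 of 5 | ≤1 of 6 (dose passes) |
|---|---|---|---|---|
| 10% | 0.028 | 0.052 | 0.081 | 0.886 |
| 20% | 0.104 | 0.181 | 0.263 | 0.655 |
| 30% | 0.216 | 0.348 | 0.472 | 0.420 |
| 40% | 0.352 | 0.525 | 0.663 | 0.233 |
| 50% | 0.500 | 0.688 | 0.813 | 0.109 |

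The chance of conflict is the second column (together) or the fourth (one at a time).

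**4. Extra exposure at 5 mg if the synopsis is obeyed.**
- Together: extra patients = 3 × P(≥2 of 3).
- One at a time: extra patients = P(≥2 of 3) + P(≥2 of 4) + P(≥2 of 5).
- Extra DLTs = p × extra patients.

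| p | Extra patients, together | Extra patients, one at a time | Extra DLTs, together | Extra DLTs, one at a time |
|---|---|---|---|---|
| 10% | 0.084 | 0.162 | 0.008 | 0.016 |
| 20% | 0.312 | 0.548 | 0.062 | 0.110 |
| 30% | 0.648 | 1.036 | 0.194 | 0.311 |
| 40% | 1.056 | 1.540 | 0.422 | 0.616 |
| 50% | 1.500 | 2.000 | 0.750 | 1.000 |

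Example at 30%, together: P(≥2 of 3) = 3 × 0.09 × 0.7 + 0.027 = 0.216. Extra patients = 3 × 0.216 = 0.648, and extra DLTs = 0.3 × 0.648 = 0.194.

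As a check, the expected number treated at the level under Section 5.2 with block entry is 3·P(≥2 of 3) + 6·[1 − P(≥2 of 3)]. This gives 5.92, 5.69, 5.35, 4.94 and 4.50 across the five rates, against a fixed 6 under the synopsis. The differences are the first column of extra patients.

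**5. Is dose selection affected?** No. A dose with 2 DLTs among its first few patients fails the 1-in-6 limit whatever happens to the rest. Under 3+3 the pass probability is P(0 of 3)·P(≤1 of 3) + P(1 of 3)·P(0 of 3). At 30% this is 0.343 × 0.784 + 0.441 × 0.343 = 0.420. The six-patient rule gives 0.7⁶ + 6 × 0.3 × 0.7⁵ = 0.420. The two agree at every rate in the table.

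**6. Phase II figures.** The exact two-stage calculation for 1/21 and 4/41 gives an early-termination probability of 0.7170 and an average sample size of 26.66 at a 5% response rate. Both match Section 12.3, and the lead-in wording does not enter into them.

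**The case against.** The strongest reply is that Section 5.2 is plainly the operative text and the synopsis a loose summary. Section 5.2 sets out the procedure dose by dose, and both dosing tables send the reader there. Section 13.2.1 requires review of all toxicity before an expansion or de-escalation decision, and DSMC confirmation before further patients are treated. Section 13.1 adds weekly safety calls and continuous review. The extra-patient figures give these controls no credit.

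The conflict can also be read more narrowly. A 6-patient cohort may simply mean its full size, and the 6 additional patients at a lower dose carry no stated minimum. Entry one at a time, with a six-week DLT window for each patient, is prescribed nowhere. Finally, the documents do not say how many lead-in patients remain to be enrolled.

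Most of this stands as to weight. The hard contradiction is the minimum of 6 at 5 mg; the lower-dose difference is softer. The block-entry figures fit the recruitment wording of Section 5.2 best. The one-at-a-time figures are an upper case, kept because the continuous stop allows a halt within the second block of three. None of this removes the conflict: no text states precedence. Section 13.2.1 does not define the stages it refers to, so when its safeguard applies depends partly on which lead-in rule is being followed.

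**Conclusion.** The concern holds and is minor. The synopsis and Section 5.2 give incompatible instructions once a second DLT is seen at 5 mg before patient 6 has entered.

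For assumed DLT rates of 10% to 50%, the chance of that is 3% to 50% with block entry and 8% to 81% with entry one at a time. Following the synopsis would add on average 0.08 to 1.50 patients (block) or 0.16 to 2.00 (one at a time) at 5 mg. These figures assume independent patients and literal adherence to the synopsis with no intervention from monitoring, so they bound the effect and do not forecast it. No inferential quantity changes.

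**What to change.** Replace the lead-in wording in the synopsis with the Section 5.2 rule: treat 3 patients, add 3 more only after 0 or 1 DLT, treat at most 6 per level, and close the dose at the second DLT. Apply it to all three doses. Optionally, add a sentence to Section 13.2.1 saying that the decision points for DSMC confirmation are those of Section 5.2.

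This is a text edit with no added patients and no change to any analysis. If lead-in enrolment is already complete, the study report should still state which rule was applied.

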1. BACKGROUND AND RATIONALE

1.1 Renal Cell Carcinoma

Incidence of renal cell carcinoma (RCC) is reported 338,000 cases worldwide. RCC has a high mortality rate, causing an estimated 144,000 death each year.¹ Approximately 30% of patients are known to have metastatic disease at the time of diagnosis and another one third develop metastatic disease throughout their disease course.²

[figure not shown]
1.2 Background on RCC Treatment

VEGF receptor tyrosine kinase inhibitors represent the standard of care treatment for renal cell carcinoma (RCC). Blocking the PD-1/PD-L1 interaction is a novel immunotherapeutic approach for the treatment of solid tumors including RCC. PD-1 inhibition has shown single-agent activity in clear cell RCC patients whose disease has progressed following VEGF pathway inhibitor therapy and nivolumab is now approved in RCC previously treated with tyrosine kinase inhibitors.³ The combination of nivolumab with the CTLA inhibitor ipilimumab also has shown promising activity in RCC.⁴ The results from a phase III clinical trial are pending. Though this new class of agents represents a very promising therapeutic strategy only a fraction of patients seems to achieve durable responses.

HDAC inhibitors induce acetylation of several histone and non-histone proteins, which contributes to a wide spectrum of anti-tumor and immunomodulatory activities of this class of agents. Pan HDAC inhibitors have shown either immunosuppressive or immunopromoting properties through modulating cytokine expression, affecting macrophage and dendritic cells, or

Figure 1: Class I HDAC inhibition decreases Treg function and may enhance immune response. Class I HDAC inhibitors induce acetylation of STAT3 by inhibiting HDAC3 or HDAC1, down regulates Foxp3 gene expression and suppresses Treg function. Class II HDAC inhibitor treatment induces Foxp3 hyper acetylation by targeting HDAC7 and HDAC 9, which leads to stabilization of Foxp3 protein and enhanced Treg function. A pan inhibitor may target Class I HDACs at a low dose and impair Treg function. At a higher dose, the pan inhibitor may target also Class II HDAC and show a dominant Treg promoting effect (Shen L and Pili R Oncoimmunology 2013).

regulating costimulation molecules. HDAC inhibitors have been also shown to induce activation of major histocompatibility complex (MHC) class I and class II proteins, and co-stimulatory molecules CD40, CD80 and CD86 (Figure 1).

response. Our group has reported that the class I HDAC inhibitor entinostat suppresses regulatory T (Treg) cell function, enhances anti-tumor immune response and facilitates cytokine and vaccine immunotherapy in murine renal cell carcinoma and prostate cancer models,

[figure not shown]
The results from the clinical trials with HDAC inhibitors in cutaneous T-cell lymphoma and large cell lymphoma patients that had led to the approval of vorinostat and romidepsin suggest that the antitumor activity these agents may be in part due to the modulation of the immune

respectively.^{5,6} This Treg suppression action does not seem to occur through a depletion mechanism. On further analysis, we observed that entinostat suppresses Foxp3 gene expression in Treg cells and inhibits suppressive function of Treg cells. Entinostat acetylates STAT 3 leading to down regulation of Foxp3. Our preclinical data have shown the synergistic effect of entinostat in combination with high dose interleukin 2 in the RENCA model. Our data also suggest that inhibitors able to modify class I HDACs (class I specific and pan) decrease Foxp3 levels in Tregs in a dose- dependent manner, whereas class II specific HDAC inhibitors did not affect Foxp3 levels. This observation suggests that only class I HDAC inhibition results in Treg suppression.^{7,8}

Based on these results, we have completed a CTEP-sponsored phase I/II clinical trial with entinostat in combination with high dose interleukin 2 in patients with RCC (NCT01038778). The phase II results have been recently reported and suggest a biological and clinical activity of this combination.⁹ The primary objectives were to evaluate the safety, tolerability and efficacy of this combination strategy. The main eligibility criteria were clear cell histology, no prior treatments, and being fit to receive high dose IL-2. The phase I portion consisted of two dose levels of entinostat (3 and 5 mg, PO every 14 days) and a fixed standard dose of IL-2 (600,000 units/kg every 8 hrs). To test our hypothesis, the fixed sample size at the phase II dose level was 36 with a type I/II error of 10%.

If 11 or more of the pts have a response, the hypothesis that the response rate is $\leq 20\%$ is rejected. Dose levels 1 and 2 were completed without DLTs and 5 mg was the phase II recommended dose for entinostat. The most common transient grade 3/4 toxicities were hypophosphatemia (16%), lymphopenia (15%), and hypocalcemia (7%). We have enrolled 47 pts (44 at dose level 2), and 37 have completed one cycle (84 days) treatment. Four patients were not evaluable. 13 patients have achieved objective response (35%; 10 PR, 3 CR). To date the median PFS is 16.1 months. Decreased Tregs have been observed following treatment. Preliminary data suggest an association of higher activated antigen presenting cells and monocytic myeloid suppressive cells (MDSCs) with objective responses. The preliminary results from this phase I/II suggest that entinostat may increase the therapeutic effect of high dose IL-2 by modulating immunosuppressive cells.

Figure 2: Entinostat enhances the anti-tumor effect of PD1 inhibition in the RENCA model. Murine renal cell carcinoma cells (RENCA) expressing luciferase were orthotopically implanted. Bioluminescence was assessed at regular intervals (see schema). Tumor bearing animals were randomized to either vehicle, anti-PD1, entinostat or combination. Endpoint tumor weights

Based on these data we have tested the effect of entinostat in combination with PD1 inhibition in a murine model of renal cell carcinoma (RENCA). As shown in figure 2, entinostat enhanced the antitumor effect of anti PD1 antibody treatment. Preliminary data also show that entinostat may inhibit the immunosuppressive activity of MDSC. These data suggest that HDAC inhibition may synergize with immune checkpoint inhibitors.

1.3 Investigational Treatment

1.3.1 Entinostat

Entinostat (SNDX-275, also known as MS-275, ZK244894 and KHK2375) is a novel, potent, orally bioavailable, class I selective histone deacetylase inhibitor (HDACi) that was licensed by Syndax from Bayer Schering Pharma. Entinostat is a substituted pyridylcarbamate with a molecular weight of 376.4 and is classified as an antineoplastic agent.

Entinostat increases the acetylation of histones and other nuclear and cytoplasmic proteins. Although the mechanisms of action are not entirely elucidated, ample evidence has demonstrated that entinostat alters chromatin structure of genes (epigenetic modulation) involved in malignancy to allow for re-expression of tumor suppressor genes, up-regulation of pro-apoptotic genes, down-regulation of cell-survival genes, and down-regulation of oncogenic signaling pathways. These events restore the ability of cells to undergo cell-cycle arrest, differentiation, and apoptosis, restore sensitivity to antineoplastic agents, and reverse malignant characteristics.

1.3.2 Ipilimumab

Ipilimumab is a fully human monoclonal IgG1κ that binds to the CTLA-4 antigen expressed on a subset of T cells from human and nonhuman primates. CTLA-4 is a negative regulator of T-cell activity. Ipilimumab is a mAb that binds to CTLA-4 and blocks the interaction of CTLA-4 with its ligands, CD80/CD86. Blockade of CTLA-4 has been shown to augment T-cell activation and proliferation, including the activation and proliferation of tumor-infiltrating T-effector cells. Inhibition of CTLA-4 signaling can also reduce Treg function, which may contribute to a general increase in T-cell responsiveness, including the anti-tumor response. Ipilimumab is currently FDA approved in the treatment of unresectable or metastatic melanoma. Ipilimumab is also under investigation for the treatment of subjects with other types of cancer. Studies are being sponsored by Bristol-Myers Squibb, with the US National Cancer Institute (NCI) and Mayo Clinic as additional sponsors.

1.3.3 Nivolumab

Nivolumab (also referred to as BMS-936558 or MDX1106) is a human monoclonal antibody (HuMAb; immunoglobulin G4 [IgG4]-S228P) that targets the programmed death-1 (PD-1) cluster of differentiation 279 (CD279) cell surface membrane receptor. PD-1 is a negative regulatory molecule expressed by activated T and B lymphocytes.* Binding of PD-1 to its ligands, programmed death-ligands 1 (PD-L1) and 2 (PD-L2), results in the down-regulation of lymphocyte activation. Inhibition of the interaction between PD-1 and its ligands promotes immune responses and antigen-specific T-cell responses to both foreign antigens as well as self-antigens. Nivolumab is expressed in Chinese hamster ovary (CHO) cells and is produced using standard mammalian cell cultivation and chromatographic purification technologies. The clinical study product is a sterile solution for parenteral administration.

OPDIVO™ (nivolumab) is approved for use in multiple countries including the United States (US, Dec-2014), the European Union (EU, Jun-2015), and Japan (Jul-2014).

*Clinical Study Report: Study No. CA209017. An Open-label Randomized Phase III Trial of BMS-936558 (Nivolumab) versus Docetaxel in Previously Treated Advanced or Metastatic Squamous Cell Non-small Cell Lung Cancer (NSCLC). Bristol-Myers Squibb Company; 2015. Document Control No. 930086504.

